8.4.2.1 Investigator Assessment of Adverse Events

The investigator will assess all AEs with respect to **seriousness** (according to SAE definition above), **severity** (intensity or grade, see below), and **causality** (relationship to study agent and relationship to participation in the research, see below).

8.4.2.1.1 Severity Grading

The investigator will grade the severity of fever (by non-oral temperature reading) and each blood laboratory testing AE according to the “Mali Adverse Event Grading Scale” provided in **APPENDIX B: MALI ADVERSE EVENT GRADING SCALE**. Events that are not gradable using this table (e.g., urinalysis abnormalities) will be graded according to the “Guidance for Industry: Toxicity Grading Scale for Healthy Adult and Adolescent Volunteers Enrolled in Preventive Vaccine Clinical Trials” which can be found at: <https://www.fda.gov/regulatory-information/search-fda-guidance-documents/toxicity-grading-scale-healthy-adult-and-adolescent-volunteers-enrolled-preventive-vaccine-clinical>

Events that are NOT gradable using either of the above specified tables will be graded as follows:

- Mild = grade 1
- Moderate = grade 2
- Severe = grade 3
- Potentially life threatening = grade 4
- Death = grade 5

Abbreviated Title: Anti-malaria MAb in Mali

Version Date: October 13, 2022

NOTE: A subject death should always be reported as grade 5.

8.4.2.1.1.1 Laboratory Value Assessment and Clinical Significance Criteria

Except as specified below, ALL abnormal lab values of grade 1 or above are REPORTABLE.

Grade 1 and 2 abnormal laboratory values are considered CLINICALLY SIGNIFICANT, and are to be recorded in the research database, and reported, if they meet ONE or more of the following criteria:

- result in a study agent dosage adjustment, interruption, or discontinuation
- are accompanied by clinically abnormal signs or symptoms that are likely related to the laboratory abnormality (e.g., clinical jaundice)
- indicate a possible organ toxicity (e.g., elevated serum creatinine)
- result in additional/repeat testing or medical intervention (procedures/treatments) (e.g., ECG to evaluate arrhythmia potential with a high serum potassium; one or more ECGs to assess an elevated troponin level; potassium supplementation for hypokalemia)
- indicates possible over-dosage
- are considered clinically significant by the investigator or SMM

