2.3 RISK/BENEFIT ASSESSMENT

2.3.1 Known Potential Risks

Risk of CIS43LS: CIS43LS is being evaluated in an ongoing phase 1 study in healthy adult volunteers at the VRC to assess safety, tolerability, PK, and protective efficacy, as described in section 2.2.2.1. Since January 2020, 25 subjects have received CIS43LS either IV or SC, and there have been no SAEs assessed as related to CIS43LS and no safety pauses. All systemic symptoms were only mild to moderate and self-limited. Mild or moderate headache was reported

Abbreviated Title: Anti-malaria MAb in Mali

Version Date: October 13, 2022

by 6 subjects (29%). Other solicited systemic AEs include mild myalgia (5 subjects), moderate malaise (1), moderate nausea (1), mild joint pain (1), and mild fever (1). There were also 3 related unsolicited AEs that were reported (blood creatinine increase, neutropenia and dizziness), all of which were graded as mild. All IV infusions were well-tolerated. Of the 12 subjects who received 40 mg/kg IV, 2 reported mild infusion-site pain or tenderness and 1 reported moderate infusion-site bruising. The protocol and consent will be updated if new information about risks and side effects becomes available from the ongoing phase 1 study.

Risks of MAb Administration: Administration of MAbs may cause immune reactions such as acute anaphylaxis, serum sickness, and the generation of antibodies. However, these reactions are rare and more often associated with MAbs targeted to human proteins or with the use of mouse MAbs that would have a risk of human anti-mouse antibodies.¹² In this regard, because CIS43LS is targeted to a parasite antigen and is a human MAb, it is expected to have a low risk of such side effects.

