8.4 SAFETY DEFINITIONS, MANAGEMENT, AND SPONSOR REPORTING

8.4.1 Definitions

Adverse Event: An AE is any untoward or unfavorable medical occurrence in a human subject, including any abnormal sign (e.g., abnormal physical exam or laboratory finding), symptom, or disease, temporally associated with the subject's participation in the research, whether or not considered related to the research.

Adverse Reaction: An AR means any AE caused (see "Causality" below) by a study agent. ARs are a subset of all suspected adverse reactions (SARs; defined below) where there is reason to conclude that the study agent caused the event.

Suspected Adverse Reaction: SAR means any AE for which there is a reasonable possibility that the study agent caused the AE.

Per US FDA guidance:

For the purposes of IND safety reporting, "reasonable possibility" means there is evidence to suggest a causal (see "Causality" below) relationship between the study agent and the AE. A SAR implies a lesser degree of certainty about causality than an AR, which means any AE caused by a study agent.

SARs are the subset of all AEs for which there is a reasonable possibility that the study agent caused (see "Causality" below) the event. Inherent in this definition, and in the requirement to report SARs, is the need for the sponsor to evaluate the available evidence and make a judgment about the likelihood that the study agent actually caused the AE.

The sponsor is responsible for making the causality judgment.

Serious Adverse Event: An SAE:

- is an AE that results in death.

Abbreviated Title: Anti-malaria MAb in Mali

Version Date: October 13, 2022

- is an AE that is life-threatening event (places the subject at immediate risk of death from the event as it occurred).
- is an AE that requires inpatient hospitalization or prolongs an existing hospitalization.

NOTE:

- Hospitalization is considered required if outpatient treatment would generally be considered inappropriate.
- Same-day surgical procedures that are required to address an AE are considered hospitalizations, even if they do not involve an overnight admission.

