8.4.2 Documenting, Assessing, Recording, and Reporting Events

ALL AEs, including those that may appear to have a non-study cause (see “Causality” below), will be documented (e.g., on the clinical chart/progress notes/clinical laboratory record), recorded (e.g., in the study-specified CRF/research database), and reported (e.g., cumulatively from the research database, or according to protocol-specified expedited reporting mechanism) to the sponsor from the time informed consent is obtained through the timeframe specified below. At each contact with the subject, information regarding AEs will be elicited by open-ended questioning and examinations.

AEs and SAEs will generally be recorded, assessed, and reported according to the timeframes outlined in [Table 2](#).

Abbreviated Title: Anti-malaria MAb in Mali

Version Date: October 13, 2022

Table 2. Standard event recording, assessment, and reporting timeframes.

Event type	Record, assess, and report through
Related SAEs	End of subject participation in study, or if study personnel become aware thereafter
Unrelated SAEs	End of subject participation in study
Related non-serious AEs of grade 1 to 3	End of subject participation in study
All other related non-serious AEs	End of subject participation in study
Unrelated non-serious AEs	End of subject participation in study

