9.4.5 Safety Analyses

Safety analysis will be primarily MITT where individuals who receive assignment but do not receive any product are excluded. Because of blinding and the brief length of time between assignment and administration, such cases will be very few.

Safety data will be presented by line listing and tables at the individual level to provide details on safety events such as severity, duration, and relationship to study product. The number and percentage of subjects with 1 or more AEs will be summarized by dose arm along with the exact 95% confidence intervals of the AE rate. For subjects experiencing more than 1 AE, the subjects will be counted once under the event of highest severity.

In the efficacy study, comparisons between the dose arms and the control arm will be additionally performed in terms of the proportions of solicited AEs, related AEs, and SAEs.

In the rare case of subjects receiving a regimen different from assignment, a per-protocol analysis will be performed as a secondary analysis, which will include subjects according to the product they actually receive in the study.

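### Recording of grade 1–2 laboratory abnormalities rests partly on judgement, and no planned analysis uses the results themselves, so mild changes, especially neutropenia, may be under-counted

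*Combined protocol and SAP*

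**What the plan says.** **Recording rules.** Section 8.4.1 defines an AE as any untoward occurrence, "including any abnormal sign (e.g., abnormal physical exam or laboratory finding"). Section 8.4.2 requires that "ALL AEs, including those that may appear to have a non-study cause" be documented, recorded and reported. Table 2 and section 8.4.2.2 set no lower limit of grade.

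**The laboratory rule.** Section 8.4.2.1.1.1 opens: "Except as specified below, ALL abnormal lab values of grade 1 or above are REPORTABLE". It then says that grade 1 and 2 values count as clinically significant, and "are to be recorded in the research database, and reported, if they meet ONE or more of the following criteria". There are six criteria. One covers values that "indicate a possible organ toxicity (e.g., elevated serum creatinine"). Another covers values that "are considered clinically significant by the investigator or SMM". A third is met when the result leads to repeat testing or an intervention.

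**Analysis.** Section 9.4.5 plans listings and an AE summary: "The number and percentage of subjects with 1 or more AEs will be summarized by dose arm". A subject with several AEs is counted once, at the highest severity. In the efficacy study the arms are compared on solicited AEs, related AEs and SAEs. Neither 9.4.5 nor the general approach in 9.4.1 names laboratory values.

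**Data available.** The efficacy schedule (1.3.2) draws CBC, ALT and creatinine on days 0, 3, 7 and 14, with the day 0 sample taken before infusion.

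**Earlier experience.** Section 2.3.1 reports "3 related unsolicited AEs that were reported (blood creatinine increase, neutropenia and dizziness), all of which were graded as mild".

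**The concern.** CBC, ALT and creatinine are objective measurements, taken on a fixed schedule and gradable from Appendix B. The plan nevertheless lets a grade 1 or 2 result reach the safety tables only as an AE, and makes its entry as an AE depend partly on what a clinician thinks or does. Two subjects with the same neutrophil count could be counted differently.

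Two of the three related unsolicited events in phase 1 were mild laboratory changes, so mild laboratory toxicity is a plausible signal here. At stake are the sensitivity of the arm comparison in the efficacy study and the completeness of the AE rates in the dose-escalation part, which has no control arm and whose safety data clear the way to the efficacy study (9.4.8).

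**Working it through.** **1. Can the recording rules be read together?** Under 8.4.1, 8.4.2 and 8.4.2.2, a grade 1 neutrophil count is an AE and is recorded. Under 8.4.2.1.1.1 it is recorded and reported if it meets a criterion. If every grade 1–2 value were recorded anyway, the list would have no effect on recording, and the opening words of that section would announce an exception that never applies. Site staff can reasonably read the list as a gate for AE entry. The sections conflict as written.

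**2. What must happen before a mild laboratory change counts?**
- To enter the count of subjects with an AE, it must pass the 8.4.2.1.1.1 criteria. Even then it is not visible there if the subject also had a more severe AE.
- To enter an arm comparison, it must also be judged related (8.4.2.1.2), since the solicited list in 6.1.2.4 contains only symptoms. That is two judgements.

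**3. Which parameters are exposed?** Raised creatinine is the section's own example of possible organ toxicity, so it should be recorded. Neutropenia has no such example. Appendix B says that it is graded and followed, but also urges caution in interpreting it.

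**4. Baseline.** Exclusion criteria 5 and 6 let investigators enrol subjects with out-of-range CBC, ALT or creatinine judged not clinically significant. Some abnormalities may therefore exist on day 0. No shift from day 0 is planned.

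**5. Size: the plan's own figure first.** Table 5 gives, for 110 per arm, a placebo rate of 1.0% and two-sided 0.025, a detectable difference of 9.7 points (1.0% vs 10.7%) at 80% power. The pooled normal approximation is

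power = Φ{[d√n − z√(2p̄(1−p̄))] / √(p₁(1−p₁) + p₂(1−p₂))}, with z = 2.2414.

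With d = 0.097 and p̄ = 0.0585: (1.0174 − 0.7439)/0.3247 = 0.842, so power is 80%. Table 5 is reproduced.

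Now let a fraction c of true events be recorded, equal in both arms, so that p₁ and p₂ become c·p₁ and c·p₂. **Every value of c below 100% is an assumption, and 1.0% is a Table 5 scenario, not an estimate.**

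| c | Rates seen (%) | Power for the same true difference | True MAb rate needed for 80% power |
|---|---|---|---|
| 100% | 1.0 vs 10.7 | 80% | 10.7% |
| 90% | 0.9 vs 9.6 | 75% | 11.6% |
| 75% | 0.75 vs 8.0 | 66% | 13.5% |
| 50% | 0.5 vs 5.4 | 46% | 19.0% |
| 25% | 0.25 vs 2.7 | 23% | 35.5% |

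**6. Dose-escalation part, 18 subjects.** The chance of recording at least one event is 1 − (1 − r·c)^18. For r, section 2.3.1 gives 25 recipients, while its 6 headaches at 29% imply about 21 (6/0.29 = 20.7), so both are shown. Neutropenia alone is 1 event. Both laboratory events make 2, if they occurred in different subjects, which is assumed.

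| c (assumed) | r = 1/25 | r = 1/21 | r = 2/25 | r = 2/21 |
|---|---|---|---|---|
| 100% | 52% | 58% | 78% | 84% |
| 50% | 30% | 35% | 52% | 58% |
| 25% | 17% | 19% | 30% | 35% |

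For example, 1 − (1 − 0.04 × 0.5)^18 = 1 − 0.98^18 = 0.30. These rates come from events that investigators had already judged related, pooled over doses and routes without a control. They only show how the loss scales.

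**The case against.** The strongest reply is that 8.4.2.1.1.1 sits within AE severity grading and can be read as a rule for AE entry alone. Section 10.8.1 keeps study data in CRFs, and nothing says that laboratory results are discarded. This stands: a reader might infer that ungated grade 1–2 results never reach the database, but the documents do not say so. Nor do they say that all results are held, so the point needs a statement. Storage alone would not close the gap, because 9.4.5 would still not use the values.

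Other points also stand:
- Clinical staff and study team are blinded in the efficacy study (6.3.2). A reader might infer a bias towards one arm, but any under-recording should be similar across arms.
- The criteria limit only grades 1 and 2, so the pausing and halting triggers based on grade 3 or greater events (8.4.5, 8.4.6) are untouched.
- The dose-escalation primary endpoint is local and systemic AEs within 7 days. Laboratory findings are not named in it, and the day 14 draw falls outside it, so the effect on that endpoint itself is unclear.
- Screening excludes most out-of-range values, and a causality judgement considers timing. This reduces mixing of old and new abnormalities, but does so case by case and not by a shift from baseline.

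**Conclusion.** The point holds as a conflict between sections and a gap in the analysis. Recording of grade 1–2 laboratory abnormalities is partly discretionary, contrary to the all-AEs rule, and no planned analysis uses the laboratory results directly. Mild changes may be under-counted, and abnormalities present on day 0 are not systematically separated from new ones. In the efficacy study this mainly costs sensitivity; in the dose-escalation part recorded rates may be too low.

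Two stronger readings are not supported. One is that under-counting will occur to a known degree: the documents give no recorded fraction, the tables above rest on assumed ones, and at 90% capture the loss of power is only about 5 points. The other is that both kinds of laboratory event seen in phase 1 would be missed: creatinine is named as a value to record, so the concern is chiefly mild neutropenia. The primary efficacy analysis is unaffected. This is an inexpensive improvement to the safety analysis.

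**What to change.** 1. **Data.** State in 8.3 or 10.8.1 that every scheduled CBC, ALT and creatinine result is held in the study database, whether or not it is reported as an AE.
2. **Recording rule.** Reconcile 8.4.2.1.1.1 with 8.4.1, 8.4.2 and 8.4.2.2 by stating that its criteria govern only the reporting of grade 1–2 values as AEs, and by adding the matching exception to the all-AEs rule.
3. **Analysis.** In 9.4.5, derive the Appendix B grade by program from every scheduled result. Tabulate by arm and by parameter the worst post-infusion grade (days 3, 7 and 14) and the shift from day 0. Compare each dose arm with placebo descriptively. The dose-escalation arms get the same tables without a comparison.
4. **Programming detail.** The grade 4 cells for low WBC, low neutrophils and creatinine (male and female) add a clinical condition, fever or dialysis, to the value. The derivation must state how a value in that range is handled when the condition is absent or unknown.

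The cost is a few extra tables from samples already scheduled, with no new visits and no larger AE-reporting workload. If some results are not now entered, data entry is added. More grade 1 findings will be shown, including low neutrophil counts for which the Appendix B caution should be repeated in a table footnote.

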8.4.2.1.2 Causality

Causality (likelihood that the event is caused by the study agents) will be assessed by the principal investigator or designee considering the factors listed under the following categories:

Definitely Related

- reasonable temporal relationship
- follows a known response pattern
- clear evidence to suggest a causal relationship
- there is no alternative etiology

Probably Related

- reasonable temporal relationship
- follows a suspected response pattern (based on similar agents)
- no evidence of a more likely alternative etiology

Possibly Related

- reasonable temporal relationship
- little evidence for a more likely alternative etiology

Unlikely Related

- does not have a reasonable temporal relationship

Abbreviated Title: Anti-malaria MAb in Mali

Version Date: October 13, 2022

AND/OR

- there is good evidence for a more likely alternative etiology

Not Related

- does not have a temporal relationship

AND/OR

- definitely due to an alternative etiology

Note: Other factors (e.g., dechallenge, rechallenge, if applicable) should also be considered for each causality category when appropriate. Causality assessment is based on available information at the time of the assessment of the AE. The investigator may revise the causality assessment as additional information becomes available.

Causality assessment will be reviewed by the sponsor. The sponsor may make a separate and final determination on the “reasonable possibility” that the event was “related” (comprising definitely, probably, and possibly related) or “unrelated” (comprising unlikely and not related) to the study agent, in keeping with applicable (US FDA) guidance on sponsor IND safety reporting.

8.4.2.2 Recording of Events

AEs will be promptly recorded in the research database, regardless of possible relationship to study interventions. If a diagnosis is clinically evident (or subsequently determined), the diagnosis rather than the individual signs and symptoms or laboratory abnormalities will be recorded as the AE. The investigator will review events regularly to ensure they have been captured correctly and to perform assessment of events individually and cumulatively to assess possible safety trends.

8.4.2.3 Investigator Reporting Responsibilities

The principal investigators and/or equally qualified designees will check daily for events that may require expedited reporting.

The principal investigators and/or equally qualified designees will also monitor all accumulating data no less than weekly, or according to superseding NIH or NIAID policy, whichever is more frequent.

Data will be reviewed by the principal investigators/designees on a regular basis for accuracy and completeness.

Data will be submitted to the sponsor in keeping with all applicable agreements and when requested, such as for periodic safety assessments, review of IND annual reports, review of IND safety reports, and preparation of final study reports.

The principal investigators and/or other study designee will ensure prompt reporting to safety oversight bodies (e.g., Clinical Safety Office [CSO], DSMB), regulatory entities, and stakeholders as specified below, and according to any additional requirements or agreements.

Abbreviated Title: Anti-malaria MAb in Mali

Version Date: October 13, 2022

8.4.2.3.1 Adverse Events

Unless otherwise specified above, AE data will be entered into the research database no less than every other week and will include all data through 1 week prior to database entry.

8.4.2.3.2 Serious Adverse Events (Expedited Reporting)

Unless otherwise specified above, all SAEs (regardless of relationship and whether or not they are also UPS) must be reported to the CSO as specified by the CSO (e.g., Research Electronic Data Capture [REDCap] system; use the Safety Expedited Report Form [SERF]/email if REDCap is not available). If the preferred/indicated mechanism for reporting is not available, the CSO/SMM should be contacted by telephone, fax, or other reasonable mechanism to avoid delays in reporting.

CSO CONTACT INFORMATION:

Clinical Safety Office

[name]

[name]

[contact]

[contact]

Email: [contact]

Unless otherwise specified above, deaths and immediately life-threatening SAEs must be reported to the CSO promptly, and no later than the **first business day** following the day of study personnel awareness.

All other SAEs must be reported to the CSO no later than the **third business day** following the day of study personnel awareness.

If an individual subject experiences multiple SAEs in a closely timed/overlapping “cause-and-effect” (cascade) sequence, the principal investigators, after careful evaluation, will report ONLY primary/precipitating event(s) individually. SAEs that are determined to be definitely secondary to other SAEs will be detailed in the narrative portion of the report of the relevant primary/precipitating SAE. A clinical rationale and findings to support such reporting should be part of the narrative.

For each SAE report, the research database entry MUST match the corresponding entries on the SAE report (e.g., start and stop dates, event type, relationship, and grade), and **must be updated if necessary** (e.g., if the SAE report was generated after the corresponding AE was entered in the research database).

Unless otherwise specified above, SAEs that have not resolved by the end of the per-protocol follow-up period for the subject are to be followed until final outcome is known (to the degree permitted by the EC-approved informed consent form). If it is not possible to obtain a final outcome for an SAE (e.g., the subject is lost to follow-up), and to update the CSO, the last known status and the reason a final outcome could not be obtained will be recorded by the investigator on an SAE report update and the CRF.

Abbreviated Title: Anti-malaria MAb in Mali

Version Date: October 13, 2022

